¹ Made by Mortals is a Community Interest Company managed by and for individuals with lived experience of services and underserved populations including the NHS and/or social care.

² There are three stages in determining eligibility under the Care Act: it must be shown that the person's needs relate to a physical or mental impairment or illness; the person must be unable to achieve at least Empowered Together (Coordinated Social Care in Prison)/ET IRAS ID: 361615 Version 1: 01/08/2025

Health Research Authority

	Realist-informed formative process evaluation:
	·
	 Adult prisoners from the control and intervention arms of the RCT, including those who have withdrawn.
	ET workers (coordinators) involved in assessment and
	 care coordination and their professional supervisors. Healthcare, prison, and local authority staff involved in delivering or supporting the social care of those in the intervention and control groups.
	The other activities in WP2 will be completed by the research team, without participant involvement.
Planned Sample Size	WP1 Activities:
	Training and supervision manual for ET workers (2 workshops):
	12 participants
	Audio, film, and blog development (6-8 workshops):
	8 participants
	WP2 Activities:
	Feasibility RCT:
	 Anticipated N to screen will be between 150 and 250 with a current estimate of 190; with 76 of these then recruited into the feasibility RCT (38 per arm)
	Realist-informed formative process evaluation:
	 An estimated 48 participants will be recruited: 20 prisoners from the control and intervention arms All ET staff: 2 ET workers and 2 supervisors 24 healthcare, prison, and local authority staff
ADDITIONAL INFOR	MATION SPECIFIC TO THE WP2 FEASIBILITY RCT
Treatment Duration	The feasibility RCT will last nine months in total. Recruitment will occur during the first six months to allow the final participants time to complete the three-month intervention.
Follow-Up Duration	The feasibility RCT will include follow-ups at 42-days (six weeks) and 90-days (three months) (±7 days) post-baseline.
Planned Trial Period	The feasibility RCT will last nine months in total.
Outcome Measures	Primary ³ :
	1. Implementation of ET at each site
	2. Recruitment (numbers screened, eligible, and recruited)

two of ten outcome domains of the Care Act (e.g., dressing, toileting); and it must be shown that the inability to achieve these outcomes has a significant impact on the person's wellbeing.

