1. BACKGROUND AND RATIONALE

1.1 Background

Prisons hold some of the most socially disadvantaged people in society (6). Prevalence of neuro-diversities (7), and mental and physical health problems, is higher amongst those living in prison than the general population (6,8,9). Those aged 60 and over are the fastest growing subgroup in prison; there are now three times as many as there were in 2002 (10). Consequently, those residing in the prison are highly likely to have complex social care needs (11). The Care Act 2014 (12) that required local authorities to be responsible for meeting social care needs in prison.

Under the terms of the Care Act and accompanying statutory guidance, from April 2015, local authorities in England have had a legal obligation to assess the need for social care to eligible people in prison and provide it accordingly. Determination of the eligibility of a person's identified needs is a three-stage process. First, it must be shown that the person's needs relate to a physical or mental impairment or illness (as opposed to, for example, their criminal record). Secondly, the adult must be unable to achieve at least two of the ten outcomes set out in the national eligibility criteria as a result of these needs. Thirdly, it must be shown that the inability to achieve these outcomes has a significant impact on the adult's wellbeing. Where a person has needs that do not meet the threshold for eligibility under the Care Act, local authorities must provide information and advice to the individual on how these can be met and prevented from getting worse.

Our previous social care needs prevalence study in men's prisons found that 8 percent of the total sample reported health problems that impacted on daily living; 10 percent of younger prisoners and 21 percent of older prisoners in the total sample reported problems maintaining activities of daily living; and 24 percent of the sample reported that their mental health had an everyday impact on their behaviour (13). Processes to identify and meet these social care needs varied considerably (13,14). There was a lack of active case finding, referral follow-up, and integration between services (13,14). Despite the Care Act, local authority involvement in care remains limited (14). A combination of pressures on local authorities (15) and a lack of active case finding and screening (16) means that few assessments and care packages are delivered, leaving many with presumed unmet care needs (13).

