2.2 Outcome Measures

Primary Outcomes

WP1:

- A training and supervision manual (nine months after project commencement)
- A fidelity of implementation tool; this will be completed by a researcher in WP2 at the end
 of the three-month intervention to assess whether the intervention has been delivered in
 accordance with the protocol and manual, and to evaluate the quality of delivery
- Audio, blog, event, film, webpage content (18 months after project commencement)

WP2:

For the feasibility RCT, the below traffic light criteria will be used in the decision-making process. However, outcomes will be reviewed as a whole, such that amber or red ratings on one or more of the objectives will not necessarily prevent progression to a full trial:

- Delivery of ET at each site (at end of feasibility RCT)
 - o Green: both sites able to deliver ET
 - o Amber: one site able to deliver ET
 - o Red: no sites able to deliver ET
- Number screened, eligible, and recruited into trial (once marked eligible from screening)
 - o Green: 60% of participants recruited
 - Amber: 40-60% of participants recruited
 - o Red: <40% of participants recruited
- Outcome measure completion rates (at 42- and 90-days ±7 days post-randomisation)
 - o Green: 80% of participants have completeness of >60%
 - o Amber: 60-80% of participants have completeness of >60%
 - o Red: <60% of participants have completeness of >60%
- Intervention adherence and fidelity (at end of feasibility RCT)
 - o Green, amber, and red ratings will be based on the bespoke fidelity tool; as such, the progression criteria will be developed once the tool has been finalised.
- Retention rates (at 90-days ±7 days post-randomisation)
 - o Green: 60% of participants
 - o Amber: 40-60% of participants

- o Red: <40% of participants
- Proportion transferred and/or released during follow-up (at 42- and 90-days ±7 days postrandomisation)

Outcome measures for the cost-effectiveness feasibility analysis will include:

- Completeness of care plans, case notes, and resource use questionnaires
- Potential cost of ET (based on data from the Personal Social Services Resource Unit)
- Assessment of the feasibility of conducting a Budget Impact Analysis (BIA)
- List of suitable variables for a social Return On Investment (ROI) analysis

Outcome measures for the realist-informed process evaluation will include:

• Refined IPT, logic model, and intervention delivery platform.

Secondary Outcomes

WP2:

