9. STATISTICS AND DATA ANALYSIS

9.1 Sample Size Calculation

WP1:

The estimated sample size for the workshops for developing the manual for ET workers is N=12, whilst that for the workshops for developing the audio, blog, and film content is N=8. These group sizes will allow for effective communication, diverse perspectives, and meaningful participation.

WP2:

For the feasibility RCT, the target sample size target is N=76 (N=38 per arm). This has been derived from use of a traffic light system to determine whether an RCT is feasible. It is based on the feasibility objectives in relation to the RAG criteria that tests against being in the RED zone (unacceptable outcome) based on an expectation of being in the GREEN zone (acceptable outcome), along with the sample size to give high power to reject being in the RED zone if the GREEN zone holds true (3). The three key feasibility objectives are to assess: (i) recruitment uptake (percent of screened patients recruited), (ii) treatment fidelity, and (iii) participant retention (follow up):

i. Based on the recruitment rate, if we assume the upper boundary of the RED zone is 40% and the lower boundary of the GREEN zone is 60% (designating unacceptable and

- acceptable recruitment respectively), the sample size required for analysis given 80% power and one-sided 5% alpha would be at least N=42 (total screened participants).
- ii. Based on treatment fidelity (defined as having completed the ET assessment and having a written management plan or having been given written resources), if we assume the upper boundary of the RED zone is 60% and the lower boundary of the GREEN zone is 80%, the sample size required for analysis given 80% power and one-sided 5% alpha would be at least N=38 (intervention only).
- iii. Based on follow-up at 90 days, if we assume the upper boundary of the RED zone is 60% and the lower boundary of the GREEN zone is 80%, the sample size required for analysis given 80% power and one-sided 5% alpha would be at least N=38 (total randomised).

The sample sizes across criteria (i)-(iii) are at different levels; (i) is at the level of screened patients, whereas (ii)-(iii) are at the level of recruited patients. To meet criteria (i) we need ns \geq 42 (although we will screen approx. ns \geq 190 (i.e. (1/0.40) × nr (76)) where 0.40 is the expected proportion uptake of the total number screened), and for (ii)-(iii), we need nr = 76 (38 per arm) based on (ii)).

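### Section 9.1 plans screening on an uptake of 40% of those screened, which is its own RED boundary, and Section 2.2 appears to rate recruitment on a different denominator

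*Protocol*

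**What the plan says.** **Section 9.1, criterion (i).** The quantity is "recruitment uptake (percent of screened patients recruited". The zones are set by "if we assume the upper boundary of the RED zone is 40% and the lower boundary of the GREEN zone is 60" percent. The requirement "given 80% power and one-sided 5% alpha would be at least N=42 (total screened participants" follows. The section says the sizing rests on being in GREEN, with high power to reject RED if GREEN is true.

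**Section 9.1, closing paragraph.** It repeats that criterion (i) works at the level of people screened. It then plans roughly 190 screened, as (1/0.40) × 76, "where 0.40 is the expected proportion uptake of the total number screened".

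**Trial Summary, Planned Sample Size.** "Anticipated N to screen will be between 150 and 250 with a current estimate of 190", of whom 76 are to be recruited.

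**Section 2.2.** The progression item is "Number screened, eligible, and recruited into trial (once marked eligible from screening"). Green is 60%, Amber 40-60% and Red below 40% of participants recruited. The rating lines do not say what the percentage is taken of.

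**Section 6.1.** Only people who score positively on the ET screen are eligible, and they then go through a further consent step. Screened and eligible people are therefore different groups.

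**The concern.** Section 9.1 holds two expectations for one quantity on one explicit denominator. The test is sized on GREEN, 60% or more of those screened. The screening workload is sized on 40% of those screened, the value the same section treats as unacceptable. If recruitment goes as planned, criterion (i) as written in 9.1 ends on the RED/AMBER line.

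Section 2.2, which holds the traffic-light criteria used for the progression decision, does not clearly use the same denominator. If it means a percentage of eligible people, it measures consent among those who screen positive. The 9.1 quantity also includes the loss from people who screen negative. Recruitment is one of the three key feasibility objectives in 9.1, and the checkpoint report is based on the progression criteria (Sections 6.9 and 13.1). If the denominator stays open until the counts are known, the rating can be chosen after the fact.

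**Working it through.** **Inputs.** RED limit p0 = 0.40, GREEN limit p1 = 0.60, one-sided alpha 0.05, power 0.80, stated n = 42, expected uptake 0.40 and target 76 (all Section 9.1); screening range 150 to 250 with estimate 190 (Trial Summary); Red below 40% and Green at 60% (Section 2.2).

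**1. Reproduce the plan's figures.** One-sample test of a proportion:

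n = [(1.645 × √(0.4 × 0.6) + 0.842 × √(0.6 × 0.4)) / 0.20]² = 37.1

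With continuity correction, n = (37.1/4) × [1 + √(1 + 2/(37.1 × 0.20))]² = 41.9, so 42. The exact binomial agrees: with 42 people, reject RED at 23 or more; type I error is 0.0375 at 40% and power is 0.803 at 60%. The screening figure is 76/0.40 = 190. Both figures are right, so the problem lies in the inputs, not the arithmetic.

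**2. Rating on the screened denominator (Section 9.1).**

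| Screened | 76 recruited as % of screened | Rating |
|---|---|---|
| 150 | 50.7% | Amber |
| 190 | 40.0% | RED/AMBER line |
| 250 | 30.4% | Red |

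Green with 76 recruits needs at most 76/0.60 = 126.7, so 126 screened, which is below the planned range. Green with 190 screened needs 0.60 × 190 = 114 recruits. Exactly 40% is Amber under Section 2.2, because Red there is below 40%; Section 9.1 calls 40% the upper edge of RED.

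As an illustration, assume exactly 190 are screened and each is recruited independently with probability 0.40. The chance of falling below 40% (75 or fewer) is then 0.47, and the chance of 114 or more is about 2 × 10⁻⁸. The exact test at n = 190 rejects RED from 88 recruits (46.3%), so the planned 76 would not reject it.

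**3. Rating on the eligible denominator (one reading of Section 2.2).** The protocol gives no screen-positive rate, so the first column is an assumed range applied to 190 screened.

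| Assumed eligible fraction | Eligible | 76 as % of eligible | Rating |
|---|---|---|---|
| 50% | 95 | 80.0% | Green |
| 60% | 114 | 66.7% | Green |
| 70% | 133 | 57.1% | Amber |
| 80% | 152 | 50.0% | Amber |
| 100% | 190 | 40.0% | RED/AMBER line |

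The switch to Green comes at 126 eligible: 76/126 = 60.3%, 76/127 = 59.8%.

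**4. What would make the two figures agree.** If 60% is consent among eligible people and 0.40 is overall yield, the implied screen-positive rate is 0.40/0.60 = 66.7%. Section 9.1 states no such rate.

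**The case against.** The best defence is that 0.40 was meant as overall yield from screening and 60% as consent among eligible people, which fits together if two-thirds screen positive. That may be what the authors intended, but Section 9.1 says otherwise: it defines the criterion on screened people, counts the 42 in screened people and repeats the level in its closing paragraph.

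The bracket in Section 2.2 may also be only a timing note, since most neighbouring items carry a timepoint in the same position. This stands. Two different denominators are likely but not proven; what is certain is that 2.2 does not name one.

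Section 2.2 also says that outcomes are judged together and that an amber or red rating need not block progression, and Section 9.2 commits to reporting numbers screened, eligible and recruited. Both ratios can therefore be computed by any reader. This lowers the stakes but does not make the rating well defined.

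Three stronger readings are tempting and are not supported:

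- **That Green is out of reach.** This holds only on the screened denominator. On the eligible denominator, recruiting as planned can be Green.
- **That the 80% power is wrong because RED would be rejected only 4.5% of the time at 40% uptake.** That 4.5% is the type I error of the exact test with 190 people at its null value. The protocol's power is conditional on 60%, and it reproduces.
- **That Section 1.1 shows 190 to be far too few.** It reports that "10 percent of younger prisoners and 21 percent of older prisoners in the total sample reported problems maintaining activities of daily living", with other rates for health and mental health problems. These are separate items from an earlier study, not the ET screen, and no combined rate is given. They cannot stand in for screen positivity.

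**Conclusion.** The point holds as an inconsistency in a stated progression criterion. On the denominator that Section 9.1 names, the planning value sits 20 percentage points below GREEN and on the RED boundary, and no screening total from 150 to 250 makes 76 recruits Green. This rests on the protocol's own figures alone. That the same data can earn a different rating under Section 2.2 rests on reading its bracket as a denominator and on an assumed eligible fraction: Green at 126 or fewer eligible of 190, Amber above that until all 190 are eligible. N=42 for 40% against 60% is correct, and N=76 comes from criterion (ii), 38 in the intervention arm doubled, so neither is in question.

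**What to change.** Before recruitment data are seen:

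1. Name one denominator for the recruitment criterion and use it in both Section 2.2 and Section 9.1(i). Eligible (ET-screen-positive) people is the reading closest to 2.2. The requirement then becomes at least 42 eligible people, which a trial that recruits 76 necessarily meets, and the team should confirm that the 40/60 limits suit consent among the eligible.
2. If screened people are kept instead, reconcile the 40/60 limits with the expected 0.40 and say in 2.2 that the percentage is of those screened. The conditional power statement can stay.
3. Write the screening target as 76 / (assumed screen-positive rate × assumed consent uptake), with both inputs stated. For example, two-thirds and 60% give 76/0.40 = 190.
4. Report the screened-to-eligible yield separately from the rated criterion.

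The cost is a wording amendment to two sections, plus a screening target whose assumptions are visible and may move it from 190. The sample size of 76 does not change.

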9.2 Statistical Analysis Plan

WP1:

The workshops for developing the training and supervision manual for workers will be recorded. The data will be analysed using realist-informed thematic approach (see below for further detail) and, along with information from a prior realist review, used to generate the manual.

WP2:

The feasibility RCT will be reported in accordance with the CONSORT 2010 statement extension to pilot and feasibility trials (59). Descriptive statistics will be reported for feasibility outcomes: numbers screened, eligible, and recruited; retention rates; measure completion rates and data quality; intervention delivery and fidelity (including univariate and bivariate analysis to assess the bespoke fidelity checklist developed in WP1); and attrition during follow-up. The data will inform a potential full RCT, with variability in candidate primary and secondary measures calculated and a sample size (power calculation) for the full RCT estimated for each. Moreover, missing data will be investigated in the feasibility RCT to determine why these are missing and what can be done to minimise missingness in the future full RCT. Simple descriptive analyses will identify the extent of missing data for various questions and questionnaires in the dataset, and models will be fitted to see whether the probability of missingness is linked to baseline characteristics. No statistical comparisons between treatment groups will be undertaken on baseline or follow-up data, as the study is not designed to test effectiveness. Adverse events will be summarised descriptively.

For the cost-effectiveness feasibility analysis, descriptive statistics including data completeness will be reported for each source. The potential cost of ET will be calculated based on information Empowered Together (Coordinated Social Care in Prison)/ET IRAS ID: 361615 Version 1: 01/08/2025

collected using the bespoke fidelity tool about time spent on training, supervision, developing care plans and other components of intervention delivery. Staff time will be costed based on unit costs from the Personal Social Services Resource Unit (60). The team will also investigate the suitability of the ASCOT SCT4, EQ-5D-5L, or ReQoL-10 to calculate the incremental cost per QALY, and the ICECAP-A for YFC gained as part of a full economic evaluation. The extent to which each outcome measure aligns with changes in the CANFOR-R and meeting of social care needs will also be evaluated.

Data will be reported on the number of participants at each stage of the study (screened, eligible, recruited, randomised, completed measures). Their characteristics and the outcome measures will be summarised through means (SD), medians (interquartile range), or Ns (%). For the ASCOT SCT4, EQ-5D-5L, ICECAP-A, and ReQoL-10, ceiling or floor effects for the summary utility score will be examined, and the proportion of participants at each level in each domain will be reported. Appropriate statistical models to determine relationships between the different patient reported outcome measures and social care outcomes will be developed to determine suitability for use in a full RCT. Descriptive statistics for resource cost and use, along with the proportion of missing data for different methods to collect resource use, will be reported to inform a full RCT.

For the process evaluation, a realist logic of analysis will be used with codes developed as linked dyads and triads directly from narratives (61). A realist-informed thematic approach to analysing field notes and transcripts will be taken (61,62). Interviews will be analysed thematically using a framework method (63). In this method, data is sifted, charted, and sorted in accordance with key issues and themes using five steps: familiarisation; identifying a thematic framework; indexing; charting; and mapping and interpretation. This produces a matrix of summarised data, providing a structure to analyse and reduce this data. It also allows for systematic constant comparisons across participants' transcripts to refine themes. It is frequently used in applied research studies where research questions are predefined. The team will produce a table of explanatory accounts. Wherever possible, expressed explanatory accounts will be in the form of 'If... then' statements that specify the context and the mechanism. The explanatory accounts will form a 'narrative' (coherent linear description of how each stage of the intervention should be refined, if applicable) which will be used to refine our logic model and intervention delivery platform.

Finally, thematic analysis (64) will be used to understand necessary modifications to evaluation design. Braun and Clarke's thematic analysis method is an iterative process consisting of six key steps: becoming familiar with the data, generating codes, generating themes, reviewing themes, defining and naming themes, and locating exemplars.

9.3 Procedure(s) to Account for Missing or Spurious Data

Reasons for being unable to collect data during assessments will be recorded on the eCRF where appropriate. eCRFs will be assessed for missing data by PenCTU, and the research team will be regularly asked to follow up missing data. The CTU will maintain a record of site compliance with eCRF completion. If data completion is poor, a monitoring visit may be scheduled.

The eCRFs will include mandatory fields and automatic flags will be displayed to users if the form is saved without these being completed. Where questions might need to be left blank, options such as 'Not Applicable' or 'Prefer not to say' will be available, to differentiate these from missing

data. Validations will be written into the study database to raise queries with specific data fields, for example, flagging if the date of a visit does not correspond to the correct timepoint.

The PenCTU data manager will write a series of R scripts to perform data tasks that will aid data completeness. These will include checking overall completeness by field of all CRFs, checking all visits have been recorded in a logical order and checking SAE forms have been completed. The scripts will be run on a weekly basis and any concerns will be raised individually with sites.

